8.3.7 REPORTING EVENTS TO PARTICIPANTS

Individuals affected by AEs will be debriefed on an individual levels and provided the opportunity to discuss additional diagnostic and therapeutic options, as applicable. These may include discontinuation of investigational therapy, targeted treatments, additional testing. When appropriate, and only if with the consent of the subjects, the primary care physician will also be debriefed and a note will be added to the electronic health record to document the findings.

There will be no sharing of AEs in aggregate, other than what publicly disclosed in publications or presentations.

8.3.8 EVENTS OF SPECIAL INTEREST Not applicable

8.3.9 REPORTING OF PREGNANCY Not applicable

8.4 UNANTICIPATED PROBLEMS

8.4.1 DEFINITION OF UNANTICIPATED PROBLEMS (UP)

The Office for Human Research Protections (OHRP) considers unanticipated problems involving risks to participants or others to include, in general, any incident, experience, or outcome that meets all of the following criteria:

- Unexpected in terms of nature, severity, or frequency given (a) the research procedures that are described in the protocol-related documents, such as the Institutional Review Board (IRB)-approved research protocol and informed consent document; and (b) the characteristics of the participant population being studied;
- Related or possibly related to participation in the research ("possibly related" means there is a reasonable possibility that the incident, experience, or outcome may have been caused by the procedures involved in the research); and
- Suggests that the research places participants or others at a greater risk of harm (including physical, psychological, economic, or social harm) than was previously known or recognized.

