1.3 SCHEDULE OF ACTIVITIES (SOA)

	Screening visit (within 30 days)	Randomization / Treatment day 1	28±3 days	60±7 180± days days	
Inclusion/Exclusion criteria and Informed Consent	x	x			
Clinical Assessment (history and physical exam)	x	X	x		
Safety laboratory tests (CBC with diff, CMP, [urine pregnancy at randomization as applicable])			x	x	
Inflammatory biomarkers (hsCRP, IL-6)	x		X		
Quality of life (QoL) assessment	x		X		
Investigational drug dispensing (education on storage and self- administration)		X for anakinra group			
Assessment for adverse events (in-person or by telephone)			x	x x	

Interleukin-1 blockade in cardiac sarcoidosis Protocol MAGiC ART

Arrhythmia assessment with 24-hour ECG Holter	х	Χ ±14 days
[Cardiac magnetic resonance]	[X]	[X] ±14 days
[Cardiac PET scan]	[X] within 60 days	[X] ±14 days

Procedures indicated in [brackets] denote additional testing done as part of the VCU Imaging Substudy.

*_indicates complete blood cell count with differential and comprehensive metabolic profile at each time point, and pregnancy test at initial visit (if applicable)

Considering the ongoing COVID-19 pandemic emergency, the PI will consider potential deviation to the protocol if needed to promote the safe conduct of the research.

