2.2 BACKGROUND

Cardiac sarcoidosis is a rare presentation of sarcoidosis involving the heart that disproportionately affects young people, more commonly African-American women than other groups. Cardiac sarcoidosis can cause serious arrhythmic complications leading to death. Corticosteroids are the standard treatment for sarcoidosis yet the evidence for efficacy is largely lacking and their use is associated with significant toxicities. *There is no proof of survival benefit* from corticosteroids and **there have been no randomized clinical trials for patients with cardiac sarcoidosis.**

There is a dearth of safe, targeted anti-inflammatory therapies for patients with cardiac sarcoidosis. Interleukin-1 is the prototypical pro-inflammatory cytokine that is involved in virtually every acute process. Studies suggest IL-1 plays a role in the pathogenesis of sarcoidosis and we have demonstrated the presence of the inflammasome, a macromolecular structure that produces cytokines including IL-1, in the granulomas of heart tissue in patients with cardiac sarcoidosis. While IL-1 plays a role in the pathogenesis of granuloma formation in sarcoidosis, the effects of IL-1 blockade have never been evaluated as a potential therapeutic agent for cardiac sarcoidosis. IL-1 blockers have been widely studied in patients with heart disease, showing a low rate of predictable complications, making it the preferred anti-inflammatory agent to be studied in cardiac sarcoidosis.

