5.2 EXCLUSION CRITERIA

Subjects will not be eligible if they meet any one of the following exclusion criteria.

- 1. Age<21 years;
- 2. Pregnancy;
- 3. Inability to obtain consent from patient or legally authorized representative;
- 4. Contraindications to treatment with Anakinra (Kineret)(i.e. prior allergic reaction to the drug or to E. coli derived products or severe allergy to latex);
- 5. Severe anemia (*Hgb<8 g/dl due to the need of more frequent blood sampling with this study*).
- 6. Acute or chronic active infections (not including treated/cured HCV with negative viral load).
- 7. Acute or chronic inflammatory disease other than sarcoidosis.
- 8. Treatment with Tumor Necrosis Factor- α blockers.
- 9. Active acute or chronic psychiatric illness that in the opinion of the investigator may prevent from complying with study instructions;
- 10. Limited English Proficiency that in the opinion of the investigator may prevent from understanding the content of the informed consent form or safely completing the study procedures.
- 11. Live vaccination within the prior month
- 12. Neutropenia (defined as absolute neutrophil count < 1,500/ml or <1,000/ml if subject is African American)
- 13. History of malignancy within the prior 5 years (with exception of basal cell skin cancer, carcinoma in-situ of the cervix or low risk prostate cancer after curative therapy)
- 14. Participation in another concurrent intervention study within 30 day or treatment with an investigational drug within 5 half-lives prior to randomization
- 15. Severe kidney disease (GFR <30 mL/min/1.73m²)
- 16. Evidence of COVID-19 within the last 60 days or recent (21 days) exposure to close personal contact with COVID-19.
- 17. [Chronic, moderate-to-severe kidney disease (GFR <60 mL/min/1.73m²) or acute kidney injury, or history of severe hypersensitivity reactions to gadolinium-based contrast agents] For VCU Imaging Substudy

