5.3 LIFESTYLE CONSIDERATIONS

There are no specific lifestyle considerations of restrictions required of patients during this study.

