7 STUDY INTERVENTION DISCONTINUATION AND PARTICIPANT DISCONTINUATION/WITHDRAWAL

7.1 DISCONTINUATION OF STUDY INTERVENTION

Reasons for discontinuation of treatment

Reasons for discontinuation of Anakinra:

- Systemic infection (sepsis)*;
- Surgery*;
- New diagnosis of cancer that requires local or systemic treatment;
- Hypersensitivity reaction (rash, anaphylaxis, arthritis);
- Severe injection site reactions*;
- Need for immunosuppressant therapy or treatment with a biologic agent (i.e. TNF-alpha blocker);
- Acute myocardial infarction or stroke*;
- Severe neutropenia (<1,000/mm3) if there is a perception of increased infectious risk by the provider*.

In the cases labelled by * treatment may be restarted by investigators after the condition is resolved.

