7.2 PARTICIPANT DISCONTINUATION/WITHDRAWAL FROM THE STUDY

Patient withdrawal

Patients may withdraw from the study at any time. The investigators can withdraw any patient at any time from the study if medically necessary. Missing data will not be inputted. The decision regarding continuation or termination of the study will be solely based on safety data. Interim analyses will be performed by the DSMB as indicated below.

It will be documented whether or not each patient completed the study. If for any reason the study treatment or observations were discontinued, the reasons will be recorded and the IRB will be informed.

Reasons for early termination of the study

The decision regarding continuation or termination of the study will be solely based on safety data, and will be made by the DSMB. Interim analyses will be performed by the DSMB.

Halting rules

The study will be temporarily suspended if any of the following conditions are met:

• Any serious adverse event that probably or definitely related to the investigational product;

- The number of subjects experiencing a *serious* adverse event considered *unrelated or only possibly related* to the investigational product exceeds 50% (after the first 3 or more subjects are enrolled);
- The number of subjects experiencing either a serious adverse event considered unrelated or only possibly related to the investigational product or a non-serious adverse event of at least moderate intensity that is probably or definitely related to the investigational product exceeds 75%.

If any of these conditions are met, the enrollment is halted until the DSMB is given the opportunity to review the data. After the assessment of the DSMB, a discussion with the PI and the Sponsor (NCATS) should be held prior to the final decision to resume or permanently stop the study.

Example of data provided to the DSMB:

- [____] of subjects with serious AE considered probably or definitely related, if >0, halting rule
- [____] of subjects with serious AE considered unrelated or only possibly related, if >50%, halting rule
- [____] of subjects with serious AE unrelated or only possibly related + [_____] number of subjects with nonserious AE of at least moderate intensity probably or definitely related, if >75%, halting rule

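### Section 8.3.9 switches off pregnancy reporting and section 7.1 omits pregnancy as a stopping reason, so an uncomplicated pregnancy conceived on anakinra has no reporting rule, no required stop and no planned outcome contact.

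*Combined protocol and SAP*

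**What the plan says.** Section 8.3.9 consists of its title and a dismissal: "8.3.9 REPORTING OF PREGNANCY Not applicable".

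Other sections assume that women able to conceive will take part. Section 5.2 excludes pregnancy but, among adults, sets only a lower age limit of 21. Section 2.2 describes a disease that "disproportionately affects young people, more commonly African-American women than other groups". The schedule in section 1.3 includes "urine pregnancy at randomization as applicable", and its footnote places the test at the initial visit. No repeat test is shown. On conduct during the study, section 5.3 states: "There are no specific lifestyle considerations of restrictions required of patients during this study".

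Section 7.1, under "Reasons for discontinuation of Anakinra", gives eight reasons, and pregnancy is not one of them. For the reasons marked with an asterisk, "treatment may be restarted by investigators after the condition is resolved". Section 7.2 adds a general power: "The investigators can withdraw any patient at any time from the study if medically necessary".

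Sections 2.3.1 and 8.2.1 report no known toxicity of anakinra in pregnancy, but say that pregnant women are excluded. Section 8.2.3 repeats that they will not be included. Participants are followed for 180 days (section 7.3), with adverse event contacts at days 28, 60 and 180 (sections 1.1 and 1.3).

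**The concern.** The entry exclusion shows that the investigators do not want a fetus exposed to anakinra. Once dosing begins, that intention has no counterpart. Section 8.3.9 is a stated rule under a heading made for this event, so a site that meets a pregnancy will look there first and find that nothing is required.

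At stake is a fetal exposure that could go unreported to the DSMB and the IRB, could continue for the rest of the 28 days, and could end without the study learning the outcome. Tolerability is part of the trial's primary objective. No analysis, power figure or efficacy conclusion depends on this point.

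**Working it through.** The plan gives no figure to reproduce. The check is a comparison of rules, followed by a count of days.

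**1. Does another rule catch an uncomplicated pregnancy conceived after randomization?**

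- Adverse event (8.3.1): requires something untoward. An uncomplicated pregnancy is not.
- Serious adverse event (8.3.2): lists a congenital anomaly, not pregnancy.
- Unanticipated problem (8.4.1): three criteria must all hold, including a suggestion of greater risk than previously known. An uncomplicated pregnancy does not by itself meet them.
- Protocol deviation (10.1.10): covers noncompliance with the protocol. Conception after a valid randomization breaches no stated requirement.
- Stopping (7.1, 7.2): pregnancy is not listed, and the withdrawal power is permissive.

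None requires a report or a stop.

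**2. When would the outcome be known?**

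Inputs: dosing on days 1 to 28 (sections 1.1 and 7.3); last planned contact at day 180; serious events recorded if they start within 30 days after participation ends (section 8.3.4). Assumption, not a document figure: 245 to 266 days from conception to term birth.

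- Earliest term birth: 1 + 245 = day 246. Latest: 28 + 266 = day 294.
- After the last contact: 246 − 180 = 66 days, to 294 − 180 = 114 days.
- Serious event start-date limit: 180 + 30 = about day 210 (approximate, because the day-180 visit tolerance is not legible in the schedule).
- Term birth after that limit: 246 − 210 = 36 days, to 294 − 210 = 84 days.
- Sensitivity, birth at 238 days: 1 + 238 = day 239, to 28 + 238 = day 266. This is still after both points.

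**3. Could existing contacts detect the pregnancy?**

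- Day 60: 60 − 28 = 32, to 60 − 1 = 59 days since conception.
- Day 180: 180 − 28 = 152, to 180 − 1 = 179 days since conception.

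They could, if the site asks.

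**4. How many participants, and how likely?**

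Randomization is 1:1 with 28 patients, so about 14 receive anakinra. The planning cohort in section 9.2 was 55% men: 14 × (1 − 0.55) = 6.3, or about 6 women. This is an upper count for those able to conceive under that sex mix. The true number is smaller and cannot be derived, because age is not given by sex (overall mean 55, range 37 to 82).

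For scale, assume 1 to 6 such women and a yearly conception rate of 2% to 10% (neither is a document figure). Expected conceptions during dosing:

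- Low: 1 × 0.02 × 28/365 = 0.0015.
- High: 6 × 0.10 × 28/365 = 0.046, or about 0.05.

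**The case against.** The strongest reply is that the gap is narrow and the event improbable, so this is a documentation matter. Much of that stands.

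A reader might infer that no rule touches any pregnancy on anakinra. The documents do not support that. A conception before randomization that the single test missed arguably breaches the pregnancy exclusion. As a deviation it would be reported to NCATS and the coordinating university, and sent to the IRB according to its policies (section 10.1.10). The gap is clear only for conception after randomization.

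A reader might also infer that harm would go unrecorded. That too is stronger than the text. A complication found by day 180 is an adverse event and is followed until it resolves or stabilizes (sections 8.3.4 and 8.3.6). Section 8.3.4 limits serious events by start date, so whether an anomaly first seen at birth falls outside the window depends on how its start is dated. A suspected drug-related anomaly that became known could still be reported under section 8.3.6 or 8.4. What is missing is any planned contact through which the study would come to know.

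Nor does the plan direct that dosing continue. Section 7.2 lets the investigator withdraw the patient, and the exclusion shows the intention. But this is discretion, and a drug described as having no known toxicity in pregnancy gives an investigator grounds to judge withdrawal unnecessary.

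Finally, no contraception rule appears in the protocol, but one could sit in the consent form, which section 10.1.1.1 says is attached as an appendix and which was not available. The manual of procedures and the DSMB charter were not available either. The point therefore does not rest on the lack of a contraception rule. If those papers do contain pregnancy instructions, section 8.3.9 contradicts them and still needs correcting.

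**Conclusion.** The concern holds for one defined case: an uncomplicated pregnancy conceived after randomization during the 28 days of dosing. For that case the protocol requires no report and no stop, and plans no contact to learn the outcome. A term birth would come roughly two to four months after the last contact. That timing rests on the assumed gestation; the conclusion survives a birth at 238 days.

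The probability is low: under the illustrative rates, at most about 0.05 expected conceptions in the whole trial. The consequence is confined to participant and fetal safety. Low probability limits the priority, but it does not make a reporting section inapplicable when the population includes women who must be tested for pregnancy at entry. The correction is worth making because it is specific and cheap.

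**What to change.** Three changes:

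1. **Section 7.1.** Add pregnancy to the reasons for discontinuing anakinra. A conception late in dosing may not be recognized before the last dose, so this mainly helps conceptions just before or early in treatment. The next change covers the rest.
2. **Section 8.3.9.** Replace the dismissal with a rule for anakinra-treated participants. Any pregnancy detected during treatment, or with estimated conception on or before the last dose plus a short washout, is reported promptly to the PI, the DSMB and the IRB. Its outcome is collected by telephone or record review, with the participant's consent. Any congenital anomaly in such a pregnancy is reported as a serious adverse event whenever it is recognized, regardless of the section 8.3.4 window. The sponsor should state the washout in days, from the label. Exclusion 14 uses "treatment with an investigational drug within 5 half-lives prior to randomization", but that concerns other investigational drugs before entry, and the documents give no half-life for anakinra.
3. **Existing contacts.** Ask women able to conceive about pregnancy at the adverse event contacts on days 28, 60 and 180.

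The cost is an IRB-approved amendment with consent wording and a decision on re-consent, one case report form page, and one question at three scheduled contacts. Contact beyond day 180, to about day 294 plus the washout, is needed only if an exposed pregnancy occurs. Conceptions later in follow-up are outside the rule. No visit or test is added.

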8.4.2 UNANTICIPATED PROBLEM REPORTING

The investigator will report unanticipated problems (UPs) to the reviewing IRB and the DSMB.

The UP report will include the following information:

- A detailed description of the event, incident, experience, or outcome;
- An explanation of the basis for determining that the event, incident, experience, or outcome represents an UP;
- A description of any changes to the protocol or other corrective actions that have been taken or are proposed in response to the UP.

To satisfy the requirement for prompt reporting, UPs will be reported using the following timeline:

- UPs that are serious adverse events (SAEs) will be reported to the IRB and to the DSMB within 5 days of the investigator becoming aware of the event.
- Any other UP will be reported to the IRB and to the DMSB within 5 days of the investigator becoming aware of the problem.

8.4.3 REPORTING UNANTICIPATED PROBLEMS TO PARTICIPANTS

There will be no prespecified reporting procedure to participants regarding UAP. Any reporting procedure would be discussed with the IRB.

Version 3.001 31 AUG 2021

9 STATISTICAL CONSIDERATIONS

9.1 STATISTICAL HYPOTHESES

• Primary Efficacy Endpoint(s):

Interval change in CRP levels from baseline to 28 days

We hypothesize that anakinra will reduce systemic inflammation as shown by CRP levels. CRP will be measured with a widely available high-sensitivity assay able to detect values in the normal range (<2 mg/l). Hs-CRP will be measured at randomization visit and again at 28±3 days. We will use ANOVA for repeated measures and assess time_x_group interaction to determine differences between changes in the anakinra on top of standard of care group versus standard of care only group.

• Secondary Efficacy Endpoint(s):

Interval change in IL-6 levels from baseline to 28 days

We hypothesize that anakinra will reduce systemic inflammation as shown by IL-6 levels. IL-6 will be measured with a widely available ELISA assay . IL-6 will be measured at randomization visit and again at 28±3 days. We will use ANOVA for repeated measures and assess time_x_group interaction to determine differences between changes in anakinra group versus control group.

Interval change in QoL scores at SAT

We hypothesize that anakinra will improve QoL scores on SAT questionnaires. QoL SAT will be measured at enrollment and again at 28±3 days. We will use ANOVA for repeated measures and assess time_x_group interaction to determine differences between changes in anakinra group versus control group

• Additional Efficacy Endpoints(s) for Imaging Substudy available at VCU

[Interval change in T2 mapping at CMR]

[We hypothesize that anakinra will reduce myocardial edema as measured by T2 mapping at CMR. T2 mapping will be completed within 30 days of randomization and again at 28 ± 14 days. We will use ANOVA for repeated measures and assess time_x_group interaction to determine differences between changes in anakinra versus control.]

[Interval change in cardiac FDG-PET inflammation signal]

[We hypothesize that anakinra will reduce myocardial inflammation as measured by cardiac PET signaling. PET signaling will be completed within 60 days of randomization and again at 28 ± 14 days. We will use ANOVA for repeated measures and assess time_x_group interaction to determine differences between changes in anakinra versus control.]

9.2 SAMPLE SIZE DETERMINATION

Using an informatics-based tool by TriNetX we ran a retrospective analysis of patients seen in the Cardiac Sarcoidosis Clinic at VCU in the past year: we identified 30 subjects with sarcoidosis who had CRP 3-20 mg/L (we excluded patients with CRP>20 mg/L as they may have had concomitant bacterial infection, and therefore could be excluded upon screening). The mean age was 55 years (range 37-82), 55% were men, and 77% were African American. The CRP was 7.64 ±3.74 mg/L (mean±standard deviation). We predict a reduction of CRP by >60% in the anakinra group and no change in standard of care only group. The Table below shows estimated power for CRP reduction between 50% and 75% in the active treatment group (on top of standard of care changes, which are expected to be close to 0), and we evaluated 3 different standard deviation (SD) values starting with 3.74 mg/l which was obtained from our VCU cohort and exploring 0.9x and 1.1x SD.

Power analysis	CRP reduction (estimated mean 7.64 mg/l)					
N=28	50%	55%	60%	65%	70%	75%
SD 3.37 mg/l	85%	91%	95%	97%	99%	>99%
SD 3.74 mg/l	77%	84%	90%	94%	97%	98%
SD 4.11 mg/l	69%	77%	84%	89%	93%	96%

9.3 POPULATIONS FOR ANALYSES

We plan to compare the 2 groups (anakinra and control) in an intention-to-treat analysis by which all patients who (1) met all inclusion/exclusion criteria and (2) were randomly assigned to one of the 2 groups were considered as 'treated' independent of whether the patients assigned to anakinra received all or some or any of the investigational treatment after randomization has been completed and treatment assigned. For exploratory purposes we will also perform a per-protocol analysis in which the individual subjects not only will need to meet conditions (1) and (2) but also (3) need to have reported compliance with >75% of investigational drug prescribed.

Version 3.001 31 AUG 2021

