4 STUDY DESIGN

4.1 OVERALL DESIGN

We designed a randomized open-label study of anakinra 100 mg daily once daily for 28 days on top of standard of care in patients with cardiac sarcoidosis, cardiac FDG uptake on PET scan, and CRP \geq 2 mg/L.

The study is composed of 2 treatment arms:

- 1. Anakinra 100 mg/0.67 mL daily subcutaneous injection on top of standard of care for 4 weeks [active treatment];
- 2. Standard of care only [control group].

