6.3 MEASURES TO MINIMIZE BIAS: RANDOMIZATION AND BLINDED ASSESSMENT

Randomization will be handled by a member of the research team not involved in the consenting process using a dedicated randomization algorithm, stratified by center (VCU / UMich) and by race/ethnicity (Caucasian / Others).

Assessment of ECG Holter and of imaging, for substudy, will be performed by operators who are blinded to treatment allocation.

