7.3 LOST TO FOLLOW-UP

The investigational treatment will be given for 28 days. Participants will be followed for 180 days. The patients are regularly followed in clinic and will be chosen for their compliance. The proposed study is also designed to be short, only 4 weeks. All study participants will receive cards with 24-hour/7-day contact number for study team members. This approach has been sufficient to achieve a 90% retention on average in prior studies of IL-1 blockade in HF at VCU.

We will also implement a patient reimbursement of \$100 for each of 3 compled study visits (Randomization Visit, 28-day Visit, and 60-day Visit) up to a total of \$300 for completion of these study visits.

We believe this may overcome some financial barriers that our patients at VCU Health and Michigan Medicine (formerly University of Michigan Health System) may experience related to the time and cost of travel. We will collect data on enrollment and retention barriers to help enhance the success of a future phase 3 trial. The power analysis has also taken into account a potential loss of data at follow up to 20%. Missing data will not be inputted.

A participant will be considered lost to follow-up if he or she fails to return for 3 scheduled visits and is unable to be contacted by the study site staff.

The following actions must be taken if a participant fails to return to the clinic for a required study visit:

- The site will attempt to contact the participant and reschedule the missed visit within 2 weeks and counsel the participant on the importance of maintaining the assigned visit schedule and ascertain if the participant wishes to and/or should continue in the study.
- Before a participant is deemed lost to follow-up, the investigator or designee will make every effort to regain contact with the participant (where possible, 3 telephone calls and, if necessary, a certified letter to the participant's last known mailing address or local equivalent methods). These contact attempts should be documented in the participant's medical record or study file.
- Should the participant continue to be unreachable, he or she will be considered to have withdrawn from the study with a primary reason of lost to follow-up.

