9.4 STATISTICAL ANALYSES

9.4.1 GENERAL APPROACH

We will compare the change using an ANOVA for repeated measures in which we assess for the significance of the interaction of treatment allocation and time interval (time_x_group interaction) using SPSS 25.0 (Chicago, IL). Additional exploratory endpoints will include absolute CRP values at 28 days, and the percentage of patients with CRP <2 mg/L at each time point. The interval change in CRP levels from baseline to 28 days will be expressed as median and interquartile range. All reporting will be in conjunction with the CONSORT statement.¹⁹

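### The set called intention-to-treat also requires that every eligibility criterion was met, and patients without a day-28 CRP in effect drop out of the primary efficacy analysis with no sensitivity check

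*Combined protocol and SAP*

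**What the plan says.** Section 9.3 defines the main set as an "intention-to-treat analysis by which all patients who (1) met all inclusion/exclusion criteria and (2) were randomly assigned to one of the 2 groups". Such patients are kept "independent of whether the patients assigned to anakinra received all or some or any of the investigational treatment". The exploratory per-protocol set repeats conditions (1) and (2) and adds a third, reported compliance above 75%. Condition (1) is therefore a working part of both definitions.

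The trial is open label: "We designed a randomized open-label study of anakinra 100 mg daily". Blinded assessment is limited in section 6.3: "Assessment of ECG Holter and of imaging, for substudy, will be performed by operators who are blinded to treatment allocation". The section does not mention eligibility decisions or analysis-set decisions.

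The primary efficacy measure is CRP change from baseline to day 28. Section 9.4.1 says: "We will compare the change using an ANOVA for repeated measures", tested through the time-by-group interaction. On missing values, section 7.2 rules out filling them in, and section 7.3 says: "The power analysis has also taken into account a potential loss of data at follow up to 20%. Missing data will not be inputted". I read the last word as imputed. Section 7.3 also cites "90% retention on average in prior studies of IL-1 blockade in HF at VCU". No sensitivity analysis for missing CRP appears in section 9.

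**The concern.** There are two separate routes by which a randomised patient can be absent from the primary efficacy comparison.

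**Eligibility.** An intention-to-treat set is fixed at randomisation. Adding an eligibility condition lets membership depend on something that may be judged later, when the arm is known and the CRP result may be known. Some criteria in section 5.2 need judgement and bear on CRP, such as active infection and inflammatory disease other than sarcoidosis. The plan does not say who decides a breach, on which data, or blind to what.

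**Missing day-28 CRP.** With two time points, a classical repeated-measures ANOVA uses only patients who have both values. Without imputation, a patient who lacks day 28 contributes nothing to the time-by-group test.

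With 14 patients per arm, one or two absences can move the estimate, and nothing keeps them balanced between arms. Section 4.2 says the pilot is to estimate the effect size for later work, so a selective loss would carry into that planning.

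**Working it through.** **Can the text remove a randomised patient?**

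- Section 9.3 makes eligibility and randomisation joint conditions. Its protective clause covers non-adherence only.
- The Schedule of Activities (1.3) checks eligibility at screening and at randomisation, and section 5.4 keeps screen failures out. If every breach is caught there, condition (1) removes nobody.
- No section fixes eligibility on pre-randomisation data or says that a breach found later leaves the patient in the set. Removal is neither planned nor prevented.

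**Inputs for the arithmetic.** N = 28 at 1:1, so 14 per arm (6.1.1). Mean CRP 7.64 mg/L, SD 3.74 mg/L, and a 60% reduction against no change in control (9.2). Alpha and sidedness are not stated, so I assume two-sided 0.05. The SD of 3.74 is the spread of CRP between patients in a clinic cohort. Using it as the SD of change is also an assumption.

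**The plan's own figure.**

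1. Target difference = 0.60 × 7.64 = 4.584 mg/L.
2. SE = 3.74 × √(1/14 + 1/14) = 1.414 mg/L.
3. 4.584/1.414 = 3.243, and 3.243 − 1.960 = 1.283, giving power of 90.0% by the normal approximation. This matches the printed 90%, and all 18 cells of the table match in the same way. The noncentral t gives 87.7%.

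The exact match therefore needs all 28 patients evaluable. A one-sided 0.05 calculation with 11 per arm comes within 2 points of every cell but does not match them all (for example 90.0% against a printed 91%).

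**Effect of losing one patient from an arm.**

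1. If one value lies 2 SD from the mean of 14, the mean of the other 13 moves by 2 × 3.74/13 = 7.48/13 = 0.575 mg/L.
2. 0.575/4.584 = 12.6%, about 13% of the target difference.
3. The direction depends on which patient is lost. If the shift is adverse, the difference becomes 4.584 − 0.575 = 4.009, the SE is 3.74 × √(1/13 + 1/14) = 1.44, and t is about 2.8 on 25 degrees of freedom. That is still significant at two-sided 5%.

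**Worst case.** Under normal changes with SD 3.74, simulated removal of the 1, 2 or 3 least favourable of 14 values shifts that arm's mean by 0.49, 0.91 or 1.29 mg/L on average. That is 11%, 20% or 28% of 4.584. These are bounds on selective loss, not expected values.

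**Missing day-28 data alone.**

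| Per arm | Normal | t |
|---|---|---|
| 14 | 90.0% | 87.7% |
| 13 | 87.8% | 85.0% |
| 12 | 85.1% | 81.8% |
| 11 | 82.0% | 78.1% |

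A 20% loss is 0.20 × 28 = 5.6 patients, leaving about 22, or 11 per arm. Compare within a column: about 2 points of any fall from the printed 90% to a t figure come from the change of method.

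**The case against.** The strongest reply is that condition (1) only describes the order of events: patients are found eligible, then randomised. Eligibility is checked twice before treatment, drug is dispensed only after baseline testing (6.2.4), and no section gives anyone discretion to remove a randomised patient. This stands as far as it goes. The defect is a gap in the wording, not a planned exclusion.

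A reader might infer that a CRP below 2 mg/L at the randomisation visit would expose patients as ineligible after allocation. The documents do not support this. Inclusion criterion 3 accepts a qualifying value from the prior 60 days, and a later low value does not undo it on the text. Whether that draw exists is also unsettled: sections 8.1.1 and 9.1 place one at randomisation, while the Schedule of Activities lists biomarkers at screening and day 28 only. The point here does not rely on it.

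A reader might also describe the stated set as eligible completers. What section 9.3 states is eligible randomised patients. The loss of non-completers is an inference from the model and the no-imputation rule, though a secure one.

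The stakes are moderate. The primary objective is feasibility and tolerability, CRP is a laboratory measurement, and section 9.4.1 commits to CONSORT reporting, which should show exclusions by arm. The risk is therefore selective inclusion, not biased measurement. Against this, section 9.4.2 names CRP change as the primary endpoint. Follow-up after stopping drug is also partly covered, since stopping treatment (7.1) is separate from withdrawal (7.2) and patients are followed to 180 days (7.3). No section, however, says that day-28 CRP is still obtained after stopping.

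**Conclusion.** The concern holds in this form. The set labelled intention-to-treat is conditional on eligibility, in an open-label trial where that judgement is not protected from knowledge of arm or outcome. Separately, patients without a day-28 CRP are in effect omitted, with no sensitivity analysis.

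The size is illustrative: 0.58 mg/L, or 13% of the 4.58 mg/L target, for one patient 2 SD from the mean of a 14-patient arm. It rests on 3.74 mg/L serving as the SD of change. The actual number removed for ineligibility may be zero.

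The lower power figures should not be attributed to the eligibility condition. They measure missing day-28 data and assume two-sided 0.05. The 20% allowance claimed in section 7.3 is not visible in the section 9.2 table, so the sponsor should state alpha, sidedness and the evaluable number used.

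**What to change.** - In section 9.3, define the main set as all randomised patients analysed in the assigned arm, whatever is later found about eligibility. Move the eligibility condition to the per-protocol set or to a sensitivity set.
- State that day-28 CRP is collected and analysed whether or not anakinra was stopped.
- Report losses by arm and reason.
- Add a sensitivity run with missing day-28 CRP set to no change. This is conservative for anakinra, because the plan expects a fall in that arm and no change in control.
- A likelihood-based model using every available CRP is optional. Patients with only pre-treatment values say little about the day-28 contrast, so it should not be presented as restoring power.

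The cost is protocol wording and one or two extra analysis runs, with no added patients or scheduled visits. The downside is that an ineligible patient kept in the main set may slightly dilute the effect. The eligible-only result would remain available alongside it.
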